4. STUDY DESIGN

4.1. Overall Design

This is a LAP to support provision of open-label mepolizumab on an individual basis to eligible subjects who participated in clinical study MEA115921 who satisfy specific requirements, including requiring a dose of prednisolone (or equivalent) of ≥ 5 mg/day for adequate control of their EGPA. Eligible subjects can initiate mepolizumab under this LAP within a 6-month period starting from completion of study MEA115921 (i.e., at Week 60) or, if the subject discontinued study MEA115921 prematurely, from the time-point that would have been Week 60 if the subject had completed the study. Initiation of mepolizumab treatment under this LAP more than 6 months after the MEA115921 Week 60 time-point will be considered on an individual subject basis by the GSK Medical Monitor.

After IRB/Ethics Committee approval is received for this protocol, the treating physician will be required to complete a 'Long-term Access Programme Subject Application Form' if he/she identifies a subject who may be eligible for treatment (a copy will be provided in the Study Reference Manual). The completed application form must be sent to GSK for review and approval by the GSK Medical Monitor to confirm the subject is eligible for treatment with mepolizumab under this LAP. Approval will be communicated to the treating physician and mepolizumab supplies provided for initiation of treatment.

Individual investigators will be responsible for identifying subjects from MEA115921 who may be eligible for treatment with mepolizumab under this LAP and for ensuring the necessary approval is obtained from GSK. In the event a subject is deemed appropriate for treatment with mepolizumab the investigator will then be responsible for ongoing benefit:risk evaluation to support continued treatment with mepolizumab irrespective of oral corticosteroid dose. It is expected that the treating physician will monitor subjects as per standard-of-care therapy (including any requirements for blood and urine tests).

Eligible subjects will receive subcutaneously administered mepolizumab at a dose of 300 mg SC every 4 weeks.

[figure not shown]

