7.1. Time and Events Table

Visits and Assessments	Screening (up to 4 weeks)	Baseline	Week 4 (±7 days)	Week 8 (±7 days)	Week 12 (±7 days)	Week 16 (±7 days)	Week 20 (±7 days)	Week 24 (±7 days)	Every 4 week treatment cycle/assessments repeated until End of Treatment	Early withdrawal ³	End of Treatment ^{3/} Follow-up (12 weeks post-last dose)
Application Form sent to GSK for approval	X										
Written Informed Consent	X										
Demography and CV risk assessment	X										
Eligibility assessment: inclusion & exclusion criteria review	X										
Baseline information		X									
Dosing with mepolizumab ^{1,2}		X	X	X	X	X	X	X			
Corticosteroid use	X	X	X	X	X	X	X	X		X	X
AE/SAE review	X	X	X	X	X	X	X	X		X	X
Urine pregnancy test (FCBP)	X	X	X	X	X	X	X	X		X	X
Documentation of Benefit:risk evaluation to support continued supply of mepolizumab ¹	X	X			X			X			

1. The treating physician should make a benefit:risk evaluation to confirm continued treatment with mepolizumab is appropriate prior to each administration. This will be documented every 12 weeks to support continued supply. Note: it is expected that the treating physician will monitor subjects as per standard-of-care therapy (including any requirements for blood and urine tests).
2. Safety monitoring of subjects is required during SC administration and for 1 hour after the end of the injections for the first three administrations, i.e., at baseline, and Weeks 4 and 8. From Week 12 onwards, subjects can be monitored following mepolizumab administration in accordance with standard of care at the site.
3. See Section 5.3

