### 7.1. Adverse Events

Adverse events will be coded using the Medical Dictionary for Regulatory Activities (MedDRA) coding dictionary. Classification of an AE as pre-, on- or post-treatment will be made with reference to the study treatment start and stop date/time and the AE onset date/time. If the AE onset date is missing or partial then the AE will be considered on-treatment unless there is evidence to the contrary (e.g. the month of the onset date is present and is less than the month of the first dose of study medication). AEs with onset up to 4 weeks after the last dose of treatment will be considered on-treatment. AEs with onset after this period will be considered post-treatment but will be assigned to the treatment previously received.

Any SAEs for screen failures, run-in failures or subjects who were enrolled but did not receive treatment will be classified as pre-treatment SAEs.

The most frequent on-treatment AEs will be defined as AEs with frequency  $\geq 3\%$  in any treatment group.

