## 9.2. Appendix 2: Study Phases and Treatment Emergent Adverse Events

### 9.2.1. Study Phases

Treatment State	Definition
Pre-Treatment	AE Start Date/Time < Study Treatment Start Date/Time
On-Treatment	Study Treatment Start Date/Time $\leq$ AE Start Date/Time $\leq$ Study Treatment Stop Date + 28 days
Post-Treatment	AE Start Date > Study Treatment Stop Date + 28 days

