### 9.4.3. Safety

Adverse Events
Drug Related AEs
AEs with relationship marked 'YES'.
AEs Leading to Permanent Discontinuation from Study Treatment or Withdrawal from the Study
AEs with action marked "Study treatment withdrawn" or withdrawn from study status marked "YES", or a response to either of these questions is missing.
AEs on Day of Dosing
AEs with an onset date equal to a study treatment dosing date and an onset time on or after the study treatment dosing time.
AE Time Since First Dose

 
If AE onset time is missing, calculate in days as follows:-           
 
If AE start date < Date of first dose of study treatment then  <math display="block">\text{Time since first dose} = \text{AE start date} - \text{Date of first dose of study treatment}</math> 
 
If AE start date ≥ Date of first dose of study treatment then  <math display="block">\text{Time since first dose} = \text{AE start date} - \text{Date of first dose of study treatment} + 1</math> 
 
Missing if AE start date or date of first dose of study treatment is missing.
 
 
 
If AE onset time is present, calculate in days, hours, minutes as  <math display="block">\text{Time since first dose} = \text{AE start date/time} - \text{Date/time of first dose of study treatment}</math> 
 

AE Duration (Days)

• If AE onset time is missing, calculate in days as AE end date – AE start date + 1

• If AE onset time is present, calculate in days, hours and minutes as AE end date/time – AE start date/time

• Missing if AE start date or end date is missing.

AEs of Special Interest

• See Section 7.2.

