### 9.7.5. Safety Tables

Safety: Tables					
No.	Population	IDSL / Example Shell	Title	Programming Notes	Deliverable [Priority]
Exposure					
3.1.	Safety	mid_mepo_egpa_lap /interim1 Table 3.1	Summary of Exposure to Study Treatment	
 
MEA116841
 
201607
 
MEA116841 + 201607
 
	IA , SAC
3.2.	Safety	mid_mepo_egpa_lap /interim1 Table 3.2	Summary of Number of Treatment Administered	
 
MEA116841
 
201607
 
MEA116841 + 201607
 
	IA , SAC
Adverse Events (AEs)					
3.3.	Safety	AE1	Summary of On-Treatment Adverse Events by System Organ Class and Preferred Term	
 
MEA116841
 
201607
 
	IA , SAC
3.4.	Safety	AE1	Summary of Post-Treatment Adverse Events by System Organ Class and Preferred Term	
 
MEA116841
 
201607
 
	IA , SAC
3.5.	Safety	AE3	Summary of Common (>=3%) Adverse Events by Preferred Term	
 
MEA116841
 
201607
 
	IA , SAC
3.6.	Safety	AE1	Summary All Drug-Related Adverse Events by System Organ Class and Preferred Term	
 
MEA116841
 
201607As 3.1 notes
 
	IA , SAC
3.7.	Safety	AE3	Summary of Adverse Events Leading to Permanent Discontinuation of Study Treatment or Withdrawal from Study by Preferred Term	
 
MEA116841
 
201607For studies with few events/participants, listing is sufficient.
 
	IA , SAC

Safety: Tables					
No.	Population	IDSL / Example Shell	Title	Programming Notes	Deliverable [Priority]
3.8.	Safety	AE15	Summary of Common (>=3%) Non-serious Adverse Events by System Organ Class and Preferred Term (Number of Participant and Occurrences)	
 
MEA116841
 
201607Common' to be defined by study/project team. For studies with very few events/participants, listing is sufficient: discuss this option with your disclosure representative.
 
	IA , SAC
3.9.	Safety	AE5A	Summary of On-Treatment Adverse Events by System Organ Class and Preferred Term and Maximum Intensity	
 
MEA116841
 
201607Common' to be defined by study/project team. For studies with very few events/participants, listing is sufficient: discuss this option with your disclosure representative.
 
	IA , SAC

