3.40.	Safety	mid_mepo_egpa_lap /interim1 Table 3.36	Summary Profile of On-Treatment Adverse Events of Special Interest: Serious Cardiac, Vascular and Thromboembolic	
 
• MEA116841
 
• 201607
 
	IA , SAC
3.41.	Safety	mid_mepo_egpa_lap /interim1 Table 3.37	Summary Profile of On-Treatment Adverse Events of Special Interest: Serious Ischemic Events	
 
• MEA116841
 
• 201607
 
	IA , SAC

Safety: Tables					
No.	Population	IDSL / Example Shell	Title	Programming Notes	Deliverable [Priority]
Exposure-Adjusted Adverse Events					
3.42.	Safety	mid_mepo_egpa_lap /interim1 Table 3.38	Summary of Exposure Adjusted On-Treatment Adverse Events	
 
• MEA116841
 
• 201607
 
	IA , SAC
3.43.	Safety	mid_mepo_egpa_lap /interim1 Table 3.39	Summary of Exposure Adjusted Most Frequent On-Treatment Adverse Events Reported by 3% or More Subjects In Any Treatment Group	
 
• MEA116841
 
• 201607
 
	IA , SAC
3.44.	Safety	mid_mepo_egpa_lap /interim1 Table 3.40	Summary of Exposure Adjusted Drug Related Adverse Events	
 
• MEA116841
 
• 201607
 
	IA , SAC
3.45.	Safety	mid_mepo_egpa_lap /interim1 Table 3.41	Summary of Exposure Adjusted On-Treatment Adverse Events Leading To Permanent Discontinuation of Study Drug or Withdrawal From Study	
 
• MEA116841
 
• 201607
 
	IA , SAC
3.46.	Safety	mid_mepo_egpa_lap /interim1 Table 3.42	Summary of Exposure Adjusted On-Treatment Serious Adverse Events	
 
• MEA116841
 
• 201607
 
	IA , SAC
3.47.	Safety	mid_mepo_egpa_lap /interim1 Table 3.43	Summary of On-Treatment Adverse Events by Age Category	
 
• MEA116841
 
• 201607
 
	IA , SAC
3.48.	Safety	mid_mepo_egpa_lap /interim1 Table 3.44	Summary of On-Treatment Adverse Events by Sex	
 
• MEA116841
 
• 201607
 
	IA , SAC
3.49.	Safety	mid_mepo_egpa_lap /interim1 Table 3.45	Summary of On-Treatment Adverse Events by Race	
 
• MEA116841
 
• 201607201607
 
	IA , SAC

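### Table 3.45 can drop an adverse event that itself stopped the next dose, because the 28-day on-treatment limit is shorter than the longest in-window dosing interval

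*SAP*

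**What the plan says.** Table 3.45 (SAP 9.7.5) is titled "Summary of Exposure Adjusted On-Treatment Adverse Events Leading To Permanent Discontinuation of Study Drug or Withdrawal From Study", so it takes on-treatment events only.

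The phase rule is in two places. SAP 7.1 states: "AEs with onset up to 4 weeks after the last dose of treatment will be considered on-treatment". It continues: "AEs with onset after this period will be considered post-treatment but will be assigned to the treatment previously received". SAP 9.2.1 defines post-treatment as "AE Start Date > Study Treatment Stop Date + 28 days".

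SAP 9.4.3 identifies a discontinuation AE from the treatment-action and study-withdrawal responses, including AEs where either response is missing. It sets no time limit. Table 3.7, the "Summary of Adverse Events Leading to Permanent Discontinuation of Study Treatment or Withdrawal from Study by Preferred Term", has no phase limit in its title, and neither does Listing 17.

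On dosing, Protocol 4.1 says: "Eligible subjects will receive subcutaneously administered mepolizumab at a dose of 300 mg SC every 4 weeks". The Time and Events Table (Protocol 7.1) prints ±7 days on each visit from Week 4 to Week 24. The later column, "Every 4 week treatment cycle/assessments repeated until End of Treatment", has no printed window.

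**The concern.** The on-treatment tail equals one nominal dosing interval, but the schedule allows a longer one. Beyond day 28, an AE's phase depends on what happens next. If another dose is given, the last-dose date moves forward and the AE is on-treatment. If the AE prevents that dose, the last-dose date stays where it was and the AE becomes post-treatment.

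For most AE tables this is a minor boundary effect. In Table 3.45 the event that decides the classification is also the event being counted, so the rule removes only events that belong in the numerator. Table 3.45 is the only exposure-adjusted display of discontinuation AEs. Protocol 9.1 says interim safety data are meant to inform the risk-benefit assessment in EGPA.

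**Working it through.** **Inputs.** Tail of 28 days (SAP 7.1, 9.2.1). Exposure = stop − start + 29 (SAP 9.4.2). Nominal interval of 28 days (Protocol 4.1). Window of ±7 days at Weeks 4 to 24 (Protocol 7.1).

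**1. The plan's own figure.** Four weeks × 7 = 28 days. Counting inclusively from start to stop + 28 gives stop − start + 28 + 1 = stop − start + 29. The exposure formula therefore carries the same 28-day tail as the phase rule.

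**2. Longest in-window interval.**
- Windows around nominal weeks from baseline, as the column headings read: (28 + 7) − (0 − 7) = 42 days for each pair from Weeks 4–8 to Weeks 20–24.
- Baseline to Week 4: 28 + 7 = 35 days.
- Window anchored on the previous dose (the anchor is not stated): 28 + 7 = 35 days.

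All exceed 28. The gap is days 29–42 (14 days, counting the visit day) or days 29–35 (7 days).

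**3. Example.** The Week 4 dose is given on day 21. Week 8 is nominally day 56, with its window open to day 63. An AE starts on day 56, which is 35 days after the last dose.
- The next dose is given on day 60: the last-dose date is day 60 or later, so the AE is on-treatment.
- The AE stops treatment: the last-dose date stays at day 21, the limit is 21 + 28 = day 49, and 56 > 49. The AE is post-treatment and leaves Table 3.45.

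**4. Does another rule rescue it?** No. The defaults to on-treatment cover a missing or partial onset date (SAP 7.1) or a missing stop date (note to SAP 9.2.1). With complete dates, neither applies.

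**5. Size.** The documents give no event counts, so the number of events lost cannot be computed. Assume onset is uniform over the final interval and visit offsets are uniform over ±7 days:
- One dose off schedule: mean days beyond 28 = 7/4 = 1.75, and 1.75/28 = 6.2%.
- Both doses off schedule: mean = ½ × 14/3 = 2.33, and 2.33/28 = 8.3%.
- The both-doses case in whole calendar days gives 7.2% without the visit day and 8.9% with it. About 47% of intervals then exceed 28 days.
- All intervals exactly 28 days: 0%.

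At the extremes, (35 − 28)/35 = 20% and (42 − 28)/42 = 33%. These apply only when the final interval would have been that long.

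**The case against.** The strongest reply is that 28 days is a deliberate, matched convention: after the final dose, numerator and person-time stop at the same point. That is true, but it does not remove the problem. Days 29–42 of every long interval that ended in another dose are inside stop − start + 29. An AE on those days that stops the next dose cannot enter the numerator. SAP 9.4.2 also says exposure is adjusted for treatment breaks, but does not say that a late dose within its window counts as a break.

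Other parts of the reply stand:
- A reader might infer that these events vanish from the report. By title, they remain in Table 3.7, Table 3.4 (post-treatment AEs) and Listing 17. Only the exposure-adjusted rate loses them.
- A reader might infer that Tables 3.7 and 3.45 must disagree. By this route they differ only if such an event occurs, and the title of Table 3.45 already signals the restriction.
- A reader might take 20% or 33%, or 28/56 = 50% after a skipped dose, as the share of all treatment-ending AEs lost. Those are worst cases for a single interval, and a skipped dose is outside the windows. AEs that began in an earlier interval, or on the dosing day, are unaffected.
- Windows are printed only to Week 24. Applying 42 days or the 6% to 8% average to later cycles is an extrapolation.
- Nothing in the SAP makes this a principal tolerability measure. It lists no endpoints (SAP 2.2) and no hypotheses (SAP 2.4).

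The layout follows an earlier interim shell that is not in the documents, so any footnote already there cannot be checked.

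**Conclusion.** The point holds for Table 3.45. Its phase limit can exclude an AE because that AE ended treatment, and the resulting bias can only lower the rate. It is probably small: about 6% to 8% of treatment-ending AEs that start in the final interval, under uniform visit offsets and uniform onset, and near zero if visits are kept close to 28 days. With few discontinuations one event can still show: if 1 of 5 fell in the gap (assumed counts), the numerator would be 20% too low.

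The documents do not support a stronger conclusion that the safety report conceals discontinuations or that its overall picture is materially wrong. The fault is a possible understatement, and a possible mismatch with Table 3.7, for which no reconciling note is specified.

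**What to change.** Keep the planned 28-day row in Table 3.45 and add one row. The added row also counts AEs that:
- the investigator flagged as leading to treatment discontinuation or study withdrawal, excluding AEs that qualify only because a response is missing; and
- started after last dose + 28 days, but no later than the end of the window for the next scheduled dose.

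State the window anchor used. For cycles after Week 24, apply the same ±7 days for counting purposes only; this does not alter the dosing schedule. Footnote the number of added events and cross-refer to Table 3.7.

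Leave the SAP 9.4.2 person-time unchanged for every subject. Extending it only for subjects with the event would make follow-up depend on the outcome. Counting without an upper limit could bring in off-drug AEs up to the 12-week follow-up visit.

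The cost is a short SAP addition, one extra row and a small programming change, using data already collected. The added row gives a slightly less favourable rate, and its person-time is short by at most 42 − 28 = 14 days for each of the few subjects concerned.

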### 9.7.6. ICH Listings

All listings will include the following study IDs unless otherwise specified:

- MEA116841
- 201607

ICH: Listings					
No.	Population	IDSL / Example Shell	Title	Programming Notes	Deliverable [Priority]
Subject Disposition					
1.	All Subjects Enrolled	ES7	Listing of Reasons for Screen Failure		IA , SAC
2.	All Subjects Enrolled	ES2 / ES3	Listing of Reasons for Study Withdrawal		IA , SAC
3.	Safety	SD2/SD3	Listing of Reasons for Study Treatment Discontinuation		IA , SAC
Protocol Deviations					
4.	Safety	DV2	Listing of Important Protocol Deviations	• MEA116841 only	IA , SAC
5.	Safety	IE3	Listing of Participants with Inclusion/Exclusion Criteria Deviations	• MEA116841 only	IA , SAC
Populations Analysed					
6.	Safety	SP3/SP3a	Listing of Participants Excluded from Any Population	Subjects screened but not included in Safety Population	IA , SAC
Demographic and Baseline Characteristics					
7.	Safety	DM2 / DM4	Listing of Demographic Characteristics		IA , SAC
8.	Safety	DM9 / DM10	Listing of Race		IA , SAC

## CONFIDENTIAL

MEA116841

ICH: Listings					
No.	Population	IDSL / Example Shell	Title	Programming Notes	Deliverable [Priority]
Exposure and Treatment Compliance					
9.	Safety	See mid_mepo_egpa_lap/interim1 Listing 10	Listing of Exposure Data		IA , SAC
10.	Safety	See mid_mepo_egpa_lap/interim1 Listing 26	Listing of Current and Previous Treatment		IA , SAC
Adverse Events					
11.	Safety	AE8	Listing of All Adverse Events		IA , SAC
12.	Safety	AE7	Listing of Subject Numbers for Individual Adverse Events		IA , SAC
13.	Safety	AE2	Listing of Relationship Between Adverse Event System Organ Classes, Preferred Terms, and Verbatim Text		IA , SAC
Serious and Other Significant Adverse Events					
14.	Safety	AE8	Listing of Fatal Serious Adverse Events		IA , SAC
15.	Safety	AE8	Listing of Non-Fatal Serious Adverse Events		IA , SAC
16.	Safety	AE14	Listing of Reasons for Considering as a Serious Adverse Event		IA , SAC
17.	Safety	AE8	Listing of Adverse Events Leading to Withdrawal from Study / Permanent Discontinuation of Study Treatment		IA , SAC
18.	Safety	See mid_mepo_egpa_lap/interim1 Listing 19	Listing of Adverse Events Defined by the Investigator as a Systemic (Non-Allergic or Allergic/Hypersensitivity) Injection Reaction		IA , SAC

ICH: Listings					
No.	Population	IDSL / Example Shell	Title	Programming Notes	Deliverable [Priority]
19.	Safety	See mid_mepo_egpa_lap/interim1 Listing 20	Listing of Adverse Events Defined by the Investigator as a Local Injection Site Reaction		IA , SAC
20.	Safety	See mid_mepo_egpa_lap/interim1 Listing 21	Listing of AEs of Systemic Reactions Meeting Anaphylaxis Criteria		IA , SAC
21.	Safety	See mid_mepo_egpa_lap/interim1 Listing 22	Listing of Potential Opportunistic Infections		IA , SAC
22.	Safety	See mid_mepo_egpa_lap/interim1 Listing 23	Listing of Serious Ischemic AEs		IA , SAC
23.	Safety	See mid_mepo_egpa_lap/interim1 Listing 24	Listing of Malignancies		IA , SAC
Corticosteroid Medication					
24.	Safety	See mid_mepo_egpa_lap/interim1 Listing 11	Listing of Corticosteroid Therapy		IA , SAC
